6.3 Strategies for Screening, Recruitment and Retention

6.3.1 Site Investigators

Screening of potential study sites/investigators will take place by reaching out directly to sites and sharing study synopsis and soliciting their interest. If a site expresses interest in the study, they will be asked to consent for study participation. Subsequently, additional information will be shared for contracting and site initiation for subject screening.

All Site Investigators will undertake subject screening/recruitment and data collection using online electronic data collection forms (eDCFs) at baseline and at weeks 8 and 24 from baseline. Periodic follow-up with the study sites will take place throughout the study observation period to ensure engagement and retention.

6.3.2 *Study Subjects*

Upon successful recruitment of the study sites, the respective Site Investigators may identify a study coordinator at their clinics. Site Investigators and/or the study coordinator will approach, screen and consent up to a maximum of 25 study-eligible Subjects sequentially within the study enrollment window. The approach may take place during the routine patient visit or via email or phone; upon establishing contact with study Subjects, they will be provided with a description of study objectives and procedures.

In the case of in-person recruitment of study Subjects, Subjects will be screened for study eligibility using the study screener. The Subjects deemed eligible for the study will then be provided with a study informed consent form. The study coordinator or Site Investigator will ensure that Subjects can read the consent form and ask questions and be given adequate time to consider the benefits/risks associated with participation in the study. An informed consent will be obtained from each subject in accordance with applicable regulations prior to participating in any study procedures.

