5.3 Treatment Effectiveness Assessments

The effectiveness of tirbanibulin treatment will be assessed from the perspective of Site Investigators as well as the Subjects. It is expected that the Site Investigator assessments will be conducted via in-person visits/encounters at baseline, Week 8 and Week 24, and when in-person assessments are not feasible (owing to COVID-related travel restrictions), the assessments

maybe done via virtual/remote visits. The same evaluator at study site shall perform all evaluations for a subject during the study, as feasible.

5.3.1 *Investigator Global Assessment (IGA):*

Site Investigators to assess the status of subject's AK in the treated area on the face or scalp using the following IGA scale, at Weeks 8 and 24. The IGA should be representative of the investigator's overall general assessment of the subject's AK and take into account the quality, as well as the quantity, of AK lesions.

Outcome Measure	Score
Completely cleared - Approximately 100% clearance of AK lesions in the treated area	0
Partially cleared - Approximately $\geq 75\%$ clearance of AK lesions in the treated area	1
Moderately cleared - Approximately 50-74% clearance of AK lesions in the treated area	2
Minimally Cleared - Approximately <50% clearance of AK lesions in the treated area	3
Not Cleared - Approximately 0% clearance, i.e., all AK lesions remained in the treated area	4

5.3.2 *Severity of Skin Photodamage*

Site Investigators will be asked to rate the severity of skin photodamage in the AK treated area (at baseline, Weeks 8 and 24), on the following 4-point Likert scale:

Outcome Measure	Score
Absent - Smooth evenly pigmented skin	0
Mild - Freckling and/or other dyspigmentation	1
Moderate - Above plus mildly rough "dry" skin, fine wrinkling and/or telangiectasias or blotchy erythema	2

Severe - Above plus pronounced “dryness” and/or dyspigmentation and/or telangiectasia or erythema, and/or wrinkling, with or without areas of actinic purpura	3
---	---

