6.1 Sample Size Considerations

No formal sample size and power calculations were undertaken. Considering the descriptive nature of the study and the feasibility of recruiting the study population, approximately 300 study Subjects from across a maximum of 50 clinical sites for the entire study has been identified as a sample to guide the planned analysis addressing the study objectives.

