6.3 General Statistical Procedures

6.3.1 Overview

Data from Site Investigators and study Subjects will be combined into one dataset. No site-specific analyses will be conducted. Validated instruments will be scored according to developer guidelines, reporting domain scores and overall summary scores, as appropriate. EPQ and other ad hoc questions will be analyzed and reported individually, based on the respective response scales. For all outcome measures, the analyses will focus on baseline, Week-8 and Week-24, as applicable.

All statistical analyses will be based on all available data assuming that all missing data are uninformative and will be conducted using appropriate statistical software, such as SAS. An interim analysis will be conducted after the completion of 8 weeks of data collection for all study Subjects. The final study analyses will be conducted after the completion of 24 weeks of data collection for all study Subjects.

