7 DATA TABLES

All patients who received at least one dose of tirbanibulin during the study observation period and had at least some data pertaining to study primary endpoints (PROs) at Week 8 will be included in **Full Analysis Set (FAS)** to facilitate the planned descriptive analysis.

Correspondingly, patients who completed the study survey at Week 8 will be included in FAS, since patients answering Week 8 survey will have completed all relevant PRO related questions.

Safety data analyses will be conducted among the **Safety Population**, that correspond to the entire study cohort that took at least one dose of tirbanibulin. Correspondingly, all patients completing the baseline survey and took at least one dose of tirbanibulin, amounting to N=300 will be included in this analysis.

Section 7.1 Patient Demographics, Perceptions & PROs (FAS Population)

Table 1.1 Population	25
Table 1.2 Patient Demographic Characteristics	26
Table 1.3 Patient Self-Assessment: AK Treatment Motivators.....	28
Table 1.4 Patient Self-Assessment: Baseline Skin Texture.....	28
Table 1.5 Patient Reported Medication Compliance.....	29
Table 1.6 SKINDEX-16: Patient Response Summary.....	30
Table 1.7 SKINDEX-16: CFB at Week-8 for Individual Items.....	36
Table 1.8 SKINDEX-16: Domain Scores.....	41
Table 1.9 Subgroup Analysis of SKINDEX-16 Domain Scores.....	42
Table 1.10 Patient Evaluation of Overall Appearance in the Original Treated Area.....	43
Table 1.11 Subgroup Analysis of Patient Evaluation of Overall Appearance in the Original Treated Area	44
Table 1.12 Treatment Satisfaction Questionnaire for Medication (TSQM-9): Patient Scores in the Original Treated Area.....	46
Table 1.13 Subgroup Analysis of TSQM-9 Patient Domain Scores	47
Table 1.14 Patient Satisfaction with Tirbanibulin in the Original Treated Area (looks/texture)	48
Table 1.15 Subgroup Analysis of Patient Satisfaction with Treatment Ability to Improve How Skin Looks in the Original Treated Area	49
Table 1.16 Subgroup Analysis of Patient Satisfaction with Treatment Ability to Improve Skin Texture in the Original Treated Area ..	51
Table 1.17 Patient Relative Satisfaction of Tirbanibulin in Comparison with Other Topical Medications for AK in the Original Treated Area	53
Table 1.18 Subgroup Analysis of Patient Relative Satisfaction of Tirbanibulin, Regarding Duration of Skin Reactions	56
Table 1.19 Subgroup Analysis of Patient Relative Satisfaction of Tirbanibulin, Regarding Severity of Skin Reactions	58

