Subgroups	Symptoms			Emotions			Functioning		
	Baseline n, Mean	Wk-8 n, Mean	P	Baseline n, Mean	Wk-8 n, Mean	P	Baseline n, Mean	Wk-8 n, Mean	P
Gender									
Male									
Female									
Age Group									
≤ 49 years									
50 – 64 Years									
≥ 65 years									
AK Treatment Location									
Face									
Scalp									
Both									
BL Fitzpatrick Skin Type									
I / II									
III / IV / V / VI									
BL Skin Photodamage									
Absent/mild									
Moderate/Severe									
BL History of Skin Cancer									
Yes									
No									
Prior Treatment Experience: Use of Cryosurgery									
Yes									
No									
Prior Treatment Experience: Use of Other Topical Treatments									
Yes									
No									
Prior Treatment Experience: Treatment Naïve at Baseline									
Yes									
No									

P-values correspond to CFB at week-8, within respective strata.

Table 1.10 Patient Evaluation of Overall Appearance in the Original Treated Area

Questions	PER1 Week 8 (N=x)	PER24_1 Week 24 (N=x)
Compared to [8 or 24] weeks ago (at the beginning of the study), how has the overall appearance of the skin in the original AK treated area changed?	Mean (SD), Median, Min, Max	Mean (SD), Median, Min, Max
1. Much Worse	n (%)	n (%)
2. Somewhat Worse	n (%)	n (%)
3. No Change	n (%)	n (%)
4. Somewhat Improved	n (%)	n (%)
5. Much Improved	n (%)	n (%)
(1 / 2) Much / Somewhat Worse	n (%)	n (%)
(3) No Change	n (%)	n (%)
(4 / 5) Somewhat / Much Improved	n (%)	n (%)

Table 1.11 Subgroup Analysis of Patient Evaluation of Overall Appearance in the Original Treated Area

Subgroups	% Somewhat/Much Improved	Week 8 n (%)	Week 24 n (%)
Gender			
Male			
Female			
p -value			
Age Group			
≤ 49 years			
50 – 64 Years			
≥ 65 years			
p -value			
AK Treatment Location			
Face			
Scalp			
Both			
p -value			
Fitzpatrick Skin Type			
I / II			
III / IV / V / VI			
p -value			
Skin Photodamage			
Absent/mild			
Moderate/Severe			
p -value			
History of Skin Cancer			
Yes			
No			
p -value			
Prior Treatment Experience: Use of Cryosurgery			
Yes			
No			
p -value			
Prior Treatment Experience: Use of Other Topical Treatments			
Yes			
No			

p -value		
Prior Treatment Experience: Treatment Naïve at Baseline		
Yes		
No		

p-values correspond to difference between strata within respective time periods.

Table 1.12 Treatment Satisfaction Questionnaire for Medication (TSQM-9): Patient Scores in the Original Treated Area

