3 /4 Minimally/ Not Cleared	n (%)	n (%)

Table 2.11 IGA Success at Week 8 in the Original Treated Area

Character	Week 8
IGA Success	N=x
No	n (%)
Yes	n (%)

Note: IGA success at Week 8, defined as an IGA score of completely cleared (0) or partially cleared (1) in AK status in the original treated area at Week 8. The denominator for the percentages is the number of patients with available data (N=XX). X patients had missing data at Week 8.

Table 2.12 Subgroup Analysis of IGA Success

% IGA Success (Completely/Partially Cleared)		Week 8 n (%)	Week 24 n (%)
Subgroups			
Gender			
Male			
Female			
p -value			
Age Group			
≤ 49 years			
50 – 64 Years			
≥ 65 years			
p -value			
AK Treatment Location			
Face			
Scalp			
Both			
p -value			
Fitzpatrick Skin Type			
I / II			
III / IV / V / VI			
p -value			
Skin Photodamage			
Absent/mild			
Moderate/Severe			
p -value			
History of Skin Cancer			
Yes			
No			
p -value			
Prior Treatment Experience: Use of Cryosurgery			
Yes			
No			
p -value			
Prior Treatment Experience: Use of Other Topical Treatments			
Yes			
No			
p -value			

Prior Treatment Experience: Treatment Naïve at Baseline

Yes

No

p-value

P-values correspond to difference between strata within respective time periods.

Table 2.13 Clinician Evaluation of Overall Appearance in the Original Treated Area

Character	Week 8 (N=x)	Week 24 (N=X)
Compared to 8 / 24 weeks ago, how has the patient's overall appearance of the skin in the original AK treated area changed?		
1. Much Worse	AK8_2	AK8_2
2. Somewhat Worse	n (%)	n (%)
3. No Change	n (%)	n (%)
4. Somewhat improved	n (%)	n (%)
5. Much Improved	n (%)	n (%)
(1/2) Much/Somewhat Worse	n (%)	n (%)
(3) No Change	n (%)	n (%)
(4/5) Somewhat/Much Improved	n (%)	n (%)

Table 2.14 Subgroup Analysis of Clinician Evaluation of Overall Appearance in the Original Treated Area

% Somewhat / Much Improved	Week 8 n (%)	Week 24 n (%)
Subgroups		
Gender		
Male		
Female		
p -value		
Age Group		
≤ 49 years		
50 – 64 Years		
≥ 65 years		
p -value		
AK Treatment Location		
Face		
Scalp		
Both		
p -value		
Fitzpatrick Skin Type		
I / II		
III / IV / V / VI		
p -value		
Skin Photodamage		
Absent/mild		
Moderate/Severe		
p -value		
History of Skin Cancer		
Yes		
No		
p -value		
Prior Treatment Experience: Use of Cryosurgery		
Yes		
No		
p -value		
Prior Treatment Experience: Use of Other Topical Treatments		
Yes		
No		

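### Change-from-baseline SEs and p-values, including those for the primary Skindex-16 change, make no allowance for clustering of patients within sites

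*SAP*

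**What the plan says.** SAP 6.1 plans "approximately 300 study Subjects from across a maximum of 50 clinical sites", and Protocol 6.3.2 lets a site recruit "up to a maximum of 25 study-eligible Subjects". SAP 6.3.1 merges investigator and patient data into a single dataset and adds: "No site-specific analyses will be conducted". Neither document names a site or clinician effect, GEE, a cluster-robust variance or an ICC. Protocol 12.3.4 lists baseline characteristics and adherence as adjustment variables but not site, and the SAP has no corresponding section.

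The primary analysis is called descriptive (SAP 6.4), but the table shells contain inference:

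- Table 1.8 (Skindex-16 domains, primary endpoint): an SE and a p-value for change at Week 8.
- Table 1.7 (Skindex-16 items): p-values for change in proportions.
- Table 1.9 (Skindex-16 by subgroup): "P-values correspond to CFB at week-8, within respective strata".
- Tables 2.8 and 2.9 (photodamage): p-values for change, overall and within strata.
- Table 2.12 (IGA success by subgroup) and many other subgroup tables: "P-values correspond to difference between strata within respective time periods".

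No test or variance method is named for any of these. Tables 1.13 and 2.16 carry the same change footnote as Table 1.9. They are set aside here because SAP 5.2 schedules the satisfaction questionnaires only at Weeks 8 and 24.

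**The concern.** Patients at one site share clinicians, local selection of who is prescribed the drug, and local practice. If their changes resemble each other more than those of patients at different sites, 300 patients carry less information than 300 independent ones. An ordinary one-sample or paired test on the pooled data then gives an SE and a p-value for mean change that are too small.

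The table most directly exposed is Table 1.8, because it reports the primary endpoint. Clinician-rated outcomes are plausibly the most strongly correlated within site, since one clinician may score many patients with the same personal threshold. At stake is the stated precision and strength of evidence for improvement, not the size of the improvement.

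**Working it through.** The plan has no figure of its own to reproduce: 300 is a feasibility number, with no alpha, power, SD or ICC. A two-sided 5% level is assumed below only to show the effect.

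**Inputs from the documents.** 300 patients and at most 50 sites (SAP 6.1); the safety analysis also expects "amounting to N=300" (SAP 7). At most 25 per site (Protocol 6.3.2). Hence:

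- 300 / 50 = 6 patients per site on average if all 50 sites enrol.
- 300 / 25 = 12 sites at the fewest.

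**Input assumed.** The ICC of the change score, 0 to 0.20.

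**Formulas**, for sites of equal size m:

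- Design effect DE = 1 + (m − 1) × ICC
- True SE / naive SE = √DE
- Effective N = 300 / DE
- True error of a nominal 5% test of mean change = 2 × [1 − Φ(1.96 / √DE)]

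Worked example, m = 25 and ICC 0.10: DE = 1 + 24 × 0.10 = 3.40; √3.40 = 1.84; 300 / 3.40 = 88; 2 × [1 − Φ(1.96 / 1.84)] = 28.8%.

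| Sites × patients | ICC | DE | SE factor | Effective N | True error |
|---|---|---|---|---|---|
| any | 0 | 1.00 | 1.00 | 300 | 5.0% |
| 50 × 6 | 0.01 | 1.05 | 1.02 | 286 | 5.6% |
| 50 × 6 | 0.05 | 1.25 | 1.12 | 240 | 8.0% |
| 50 × 6 | 0.10 | 1.50 | 1.22 | 200 | 11.0% |
| 50 × 6 | 0.20 | 2.00 | 1.41 | 150 | 16.6% |
| 12 × 25 | 0.01 | 1.24 | 1.11 | 242 | 7.8% |
| 12 × 25 | 0.05 | 2.20 | 1.48 | 136 | 18.6% |
| 12 × 25 | 0.10 | 3.40 | 1.84 | 88 | 28.8% |
| 12 × 25 | 0.20 | 5.80 | 2.41 | 52 | 41.6% |

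A simulation of the naive one-sample test (2,000 runs per setting) agrees. At ICC 0.10 it gave 10.0% to 11.7% for 50 × 6 and 27.7% to 29.3% for 12 × 25.

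**Uneven enrolment.** Fifty sites do not guarantee the milder rows. If 10 sites enrol 25, 10 enrol 2 and 30 enrol 1 (250 + 20 + 30 = 300), the size-weighted mean is (10 × 625 + 10 × 4 + 30 × 1) / 300 = 21.1. Using that for m, the error at ICC 0.05 is 16.6%.

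**Change within a stratum (Tables 1.9 and 2.9).** Fewer patients per site fall in each stratum, so the inflation is smaller at the same ICC. If a stratum holds half of each site, m is 3 or 12.5, and at ICC 0.10 DE is 1 + 2 × 0.10 = 1.20 or 1 + 11.5 × 0.10 = 2.15.

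**Between-strata tests (such as Table 2.12).** These behave differently. Simulated naive error over ICC 0.05 to 0.20:

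| How the subgroup factor is distributed | True error |
|---|---|
| Balanced within sites | 2.5% to 5.6% |
| Random within sites | 4.5% to 5.0% |
| Mildly clustered by site | 4.9% to 8.7% |
| Same for all patients at a site | 8% to 43% |

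**The case against.** The strongest reply is that the plan is silent rather than mistaken. It names no test, and the sentence in SAP 6.3.1 can be read simply as promising no per-site results. That is correct: the sentence does not say that variances ignore site. But with no clustering provision anywhere, ordinary tests on the pooled data are the natural way to fill these shells.

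It can also be said that the study is descriptive, with no alpha, power or success rule. This stands, and it limits the consequence. It does not explain why the primary table then prints an SE and a p-value.

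A reader might infer more than the documents support:

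- **That every SE and p-value in the SAP is wrong.** Many p-values compare strata on patient-level factors such as sex, age and skin type, which can vary within a site. Those tests stay near 5% or below unless the factor clusters by site.
- **That the overall IGA and clinician-satisfaction results carry false precision.** Table 2.11 is counts and percentages, Table 2.15 has no SE or p-value, and photodamage change has p-values but no SE. No confidence interval is planned.
- **That up to 25 patients share one rater.** The cap is per site; patients per clinician are not stated. SAP 5.3 asks only that "The same evaluator at study site shall perform all evaluations for a subject during the study, as feasible". Where that is followed, a rater's constant leniency tends to cancel from photodamage change, which leaves only differences in how change is judged. Rater effects do not arise for Skindex-16, which patients complete themselves.
- **That the true error is about 42%.** That needs 12 full sites and an ICC of 0.20 together.

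**Conclusion.** The point holds in a limited form. The SAP gives no allowance for site clustering in the SEs and p-value for Skindex-16 change (Table 1.8) or in the other change-from-baseline p-values (Tables 1.7, 1.9, 2.8 and 2.9). Computed as if patients were independent, they are too small for any positive within-site correlation of the change.

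Over an assumed ICC of 0.01 to 0.10, SEs of overall change are too small by a factor of 1.02 to 1.22 with 50 equal sites, and 1.11 to 1.84 with 12 full sites. The corresponding error rates are about 5.6% to 11% and 7.8% to 29%. The documents give neither the ICC nor the enrolment per site, so the effect may be nil or substantial. The figures also assume 300 analysed patients; the FAS is limited to those who completed the Week 8 survey, so site sizes in the analysis may be somewhat smaller.

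This should be corrected, but it does not undermine the study.

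**What to change.** Add to SAP 6.3.1:

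- SEs and p-values for change from baseline treat site as the cluster, using a small-sample-corrected cluster-robust variance, for example GEE with an independence working correlation. For consistency, the subgroup p-values do the same.
- The number of sites, the distribution of patients per site and the ICC of each change outcome are reported.
- The statement on site-specific analyses means that no per-site results are shown.
- Strata with too few sites for a reliable robust variance are reported without a p-value, with the minimum number fixed before database lock.

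The independence working correlation keeps the planned mean changes and proportions as they are, so only SEs and p-values move. The tests need naming in any case. Dropping the SEs and p-values, in line with the descriptive aim, would also resolve the point.

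The cost is a short SAP addition and different procedure calls, with no new data. SEs become wider, p-values become larger, and some sparse strata lose their p-value.

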6.3.2 Summary Statistics

The descriptive statistics for all the continuous variables will include the mean, median, 25th percentile, 75th percentile, standard deviation (SD), minimum, maximum, and number of Subjects. Descriptive summaries will be provided for raw, CFB, and %CFB values for relevant endpoints, where applicable. Frequency distributions for all the categorical variables will be presented as counts and percentages. Summaries will be provided by encounters, as appropriate. Results from the descriptive analyses will be presented as summary tables and figures.

6.3.3 Subgroup Analysis

Primary, secondary, and additional (non-safety) endpoints may be summarized and repeated for the following subgroups, if sample size permits, using FAS:

- Gender: male and female
- Age groups: ≤ 49 years, 50-64 years, and ≥ 65 years.
- Fitzpatrick skin type: I/II, and III/IV/V/VI.
- Skin photodamage at baseline: absent/mild, moderate/severe.
- History of skin cancer: yes and no.
- AK Treatment location: face only, scalp only, both face & scalp.
- Prior treatment experience, as applicable:
 - Cryosurgery vs. all others;
 - Other topical treatments vs. all others;
 - Treatment naïve vs. all others.

Subgroup analyses based on patient retreatment status between Week-8 and Week-24 visits (Klisyri vs. other topicals vs. non topicals vs. not retreated) may be considered for relevant outcome measures, based on data availability.

Subgroup analyses will either assess the difference in outcomes within a specific strata at a given time period (for measures collected only at Week-8 and/or Week-24), or assess CFB within a specific strata (for measures collected at baseline and at Week-8 and/or week-24).

6.4 Primary Endpoint Analysis

The primary endpoint of PROs measured using Skindex-16 at Week 8 will be assessed descriptively using the FAS dataset.

The individual item and domain/subscale scores of Skindex-16 will be created per instrument developer instructions, analyzed descriptively (ie, using mean, SD, median, minimum and maximum), for the baseline and Week 8 encounters, treating the responses as categorical

variables and/or continuous variable, as appropriate. CFB in Skindex-16 score will be explored and reported using descriptive statistics. For the overall questionnaire data evaluation, no missing data imputation will be applied to compute domain/subscale scores.

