5.3.3 Cosmetic Appearance of Skin

Subjects and Site Investigators will be asked to rate current ‘overall appearance of the skin’ in the AK treated area (at Weeks 8 and 24, in comparison to baseline), on the following 5-point Likert scale: 1: much worse; 2: somewhat worse; 3: no change; 4: somewhat improved; 5: much improved.

Subjects will be asked to state how often has he/she been bothered by the appearance of the skin, at Baseline and Week 8, using item # 7 in Skindex-16 questionnaire. This item however will not be analyzed individually but assessed as part of emotions subscale of Skindex-16.

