PT2: How satisfied are you with this treatment's ability to improve your skin texture (i.e., how your skin feels in terms of roughness, bumpiness, scaliness) as a result of the treatment, in the original AK treated area?		
	Mean (SD), Median,Min,Max	Mean (SD), Median,Min,Max
1. Extremely Dissatisfied	n (%)	n (%)
2. Very Dissatisfied	n (%)	n (%)
3. Dissatisfied	n (%)	n (%)
4. Somewhat Satisfied	n (%)	n (%)
5. Satisfied	n (%)	n (%)
6. Very Satisfied	n (%)	n (%)
7. Extremely Satisfied	n (%)	n (%)
(1 / 2) Extremely/Very Dissatisfied	n (%)	n (%)
(3 / 4 / 5) Dissatisfied/Somewhat Satisfied/Satisfied	n (%)	n (%)
(6 / 7) Very/Extremely Satisfied	n (%)	n (%)

Table 1.15 Subgroup Analysis of Patient Satisfaction with Treatment Ability to Improve How Skin Looks in the Original Treated Area

% Extremely/Very Satisfied	Week 8 n (%)	Week 24 n (%)
Subgroups		
Gender		
Male		
Female		
p -value		
Age Group		
≤ 49 years		
50 – 64 Years		
≥ 65 years		
p -value		
AK Treatment Location		
Face		
Scalp		
Both		
p -value		
Fitzpatrick Skin Type		
I / II		
III / IV / V / VI		
p -value		
Skin Photodamage		
Absent/mild		
Moderate/Severe		
p -value		
History of Skin Cancer		
Yes		
No		
p -value		
Prior Treatment Experience: Use of Cryosurgery		
Yes		
No		
p -value		
Prior Treatment Experience: Use of Other Topical Treatments		
Yes		
No		

p -value		
Prior Treatment Experience: Treatment Naïve at Baseline*		
Yes		
No		
p -value		

P-values correspond to difference between strata within respective time periods.

Table 1.16 Subgroup Analysis of Patient Satisfaction with Treatment Ability to Improve Skin Texture in the Original Treated Area

% Extremely/Very Satisfied	Week 8 n (%)	Week 24 n (%)
Subgroups		
Gender		
Male		
Female		
p -value		
Age Group		
< 49 years		
50 – 64 Years		
≥ 65 years		
p -value		
AK Treatment Location		
Face		
Scalp		
Both		
p -value		
Fitzpatrick Skin Type		
I / II		
III / IV / V / VI		
p -value		
Skin Photodamage		
Absent/mild		
Moderate/Severe		
p -value		
History of Skin Cancer		
Yes		
No		
p -value		
Prior Treatment Experience: Use of Cryosurgery		
Yes		
No		
p -value		
Prior Treatment Experience: Use of Other Topical Treatments		
Yes		
No		

p -value		
Prior Treatment Experience: Treatment Naïve at Baseline		
Yes		
No		

P-values correspond to difference between strata within respective time periods.

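### The SAP text is descriptive and names no test, alpha or multiplicity rule, yet its shells carry 601 p-value cells in 26 tables, 562 of them conditional subgroup cells

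*SAP*

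**What the plan says.** SAP 6.4 says of the primary endpoint: "The primary endpoint of PROs measured using Skindex-16 at Week 8 will be assessed descriptively using the FAS dataset". On change from baseline it adds: "CFB in Skindex-16 score will be explored and reported using descriptive statistics". SAP 6.1 states "No formal sample size and power calculations were undertaken" and settles on "approximately 300 study Subjects from across a maximum of 50 clinical sites for the entire study", giving feasibility and "Considering the descriptive nature of the study" as the reasons. SAP 6.3.2 lists summary statistics only and says "Results from the descriptive analyses will be presented as summary tables and figures".

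SAP 6.3.3 allows the non-safety endpoints to be repeated in subgroups where sample size is sufficient. It describes two kinds of contrast: differences between strata at a visit, and change from baseline within a stratum.

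The section 7 shells contain p-value rows and columns. Their footnotes name the contrast but not the test, for example "P-values correspond to difference between strata within respective time periods". On Skindex-16 item 7, SAP 5.3.3 says: "This item however will not be analyzed individually but assessed as part of emotions subscale of Skindex-16".

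**The concern.** The text and the tables describe different analyses. A programmer following the text would print summaries. One following the shells would print hundreds of p-values and would have to choose the test, including paired or unpaired, possibly after seeing the data. Protocol section 12 defers the methods to the SAP, and SAP section 6 repeats that deferral instead of supplying them. The only inferential methods named are the Pearson correlations and unspecified multivariate analyses in protocol 12.3.4, and neither defines the tabulated p-values.

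What is at stake is interpretation. With no hypotheses, no size justification and no error control, some subgroup comparisons will fall below any conventional threshold by chance, and nothing in the plan tells the reader how to take them.

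**Working it through.** The plan gives no number of tests, alpha or power to reproduce. Its only figure is about 300 subjects, with no calculation behind it. The check is therefore a count of the shells. The 0.05 level below is my assumption.

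**Inputs.** The subgroup shells use nine factors: gender, age, location, Fitzpatrick type, photodamage, skin cancer history and three prior-treatment factors. They give 2+3+3+2+2+2+2+2+2 = 20 strata.

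**Count by layout.**
- Table 1.7: 16 items × 2 response groups = 32
- Table 1.8: 3 domains = 3
- Table 2.8: 2 dichotomies × 2 visits = 4
- Table 1.9: 20 strata × 3 domains = 60
- Tables 1.13 and 2.16: 60 each = 120
- Table 2.9: 20 strata × 2 visits = 40
- Between-strata tables (1.11, 1.15, 1.16, 1.18–1.22, 1.27, 2.12, 2.14, 2.18, 2.19, 2.21–2.25, 2.34): 19 × 9 factors × 2 visits = 342

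Total: 32 + 3 + 4 + 60 + 120 + 40 + 342 = 601 cells, in 7 + 19 = 26 tables. The Skindex-16 share is 32 + 3 + 60 = 95.

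**Legible count.** Thirteen of the 19 between-strata shells show no p-value row for the last factor (13 × 2 = 26 cells). Two cells of Table 1.7 (items 15 and 16) are broken in the extracted text. 601 − 26 − 2 = 573.

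**Unconditional and conditional.** Tables 1.7, 1.8 and 2.8 give 32 + 3 + 4 = 39 unconditional cells. The remaining 601 − 39 = 562 fall under the sample-size condition of SAP 6.3.3, which sets no threshold.

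**Cells that cannot be computed as labelled.**
- Tables 1.13 and 2.16 plan change from baseline in TSQM scores. SAP 5.2 administers TSQM-9 and the clinician version only at Weeks 8 and 24, so these 120 cells have no baseline.
- The ten relative-satisfaction tables (1.18–1.22, 2.21–2.25) rest at Week 8 on prior topical users only. Prior topical use (yes/no) and treatment-naïve (yes/no) then each have an empty stratum: 10 × 2 = 20 cells.

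601 − 120 − 20 = 461.

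**Expected by chance.** Expected number below 0.05 = m × 0.05 if every null is true. This needs valid tests but not independence. I apply it only to between-strata cells, because a no-change null is not credible in a single treated arm.
- All between-strata cells except the empty-stratum ones: 342 − 20 = 322; × 0.05 = 16.1.
- Also leaving out the Week-24 columns of the ten relative-satisfaction tables (10 × 9 = 90), where the group may be too small: 322 − 90 = 232; × 0.05 = 11.6.

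**Within-stratum p-values.** The 60 + 40 = 100 cells in Tables 1.9 and 2.9 test change inside each stratum. A small p-value in one stratum and a large one in the other is not a test that the strata differ. In Table 2.9 the photodamage strata also start at 100% or 0% absent/mild by construction, so change can go only one way.

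**Item 7.** SAP 5.3.3 rules out individual analysis, while SAP 6.4 plans individual item scores. Table 1.6 reports item 7 and Table 1.7 gives it two p-values.

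**Reference for a reduced set.** Three unadjusted tests at 0.05, if independent, give a familywise error of 1 − 0.95³ = 14.3%.

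**The case against.** The strongest reply is that 562 of the 601 cells are optional and that SAP 6.3.3 does declare the subgroup contrasts, so only the tests are undefined. That is correct. But with no threshold for adequate numbers, the condition does not limit what is printed.

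A reader might infer that about 600 p-values will be produced and that 0.05 × 601, about 30, will be false positives. The documents do not support this: most cells are conditional, at least 140 cannot be computed, and many test change after treatment, where the null is probably false.

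A reader might also count the 90 Week-24 relative-satisfaction cells as impossible. They are not. SAP 5.2, 5.4.2, 5.4.3 and 6.6.5 plan Week-24 ratings for subjects retreated with another topical, and Tables 1.31 and 2.41 tabulate them. The group may be small, which is why a range is given above.

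It can also be said that hundreds of unadjusted intervals carry the same multiplicity if readers only check whether they exclude zero. This stands, and it is why the intervals need an explicit label. The item 7 conflict is a separate text inconsistency that deleting p-values would not cure.

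**Conclusion.** The point holds. The shells contradict the SAP's descriptive text and would print uncontrolled p-values, up to about 461 of them once cells that cannot be computed are removed. About 12 to 16 of the between-strata p-values would be expected below 0.05 if no strata differ. That figure assumes a 0.05 level, production of all the workable between-strata cells, and tests that hold their nominal level. Clustering could push it higher: protocol 6.3.2 allows up to 25 subjects per site, and no method for clustering is stated.

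It would be tempting to say that chance findings will be reported as effects. The documents set no significance threshold and do not say how p-values will be interpreted, so the supportable statement is that they may be read that way. The descriptive estimates themselves remain usable.

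**What to change.** - Delete the p-value rows and columns from Tables 1.7, 1.9, 2.9 and the 19 between-strata tables. Print the estimate or difference with a 95% confidence interval, labelled exploratory and unadjusted for multiplicity.
- Remove the baseline and p-value columns from Tables 1.13 and 2.16, and the empty-stratum rows at Week 8 from the ten relative-satisfaction tables.
- If any p-values are kept, limit them to the three Skindex-16 domain changes in Table 1.8, using a pre-named paired test (for example the paired t-test) with Holm adjustment at two-sided 0.05. This limit also removes the four in Table 2.8.
- Reconcile SAP 5.3.3 with SAP 6.4 and Tables 1.6 and 1.7 on item 7.

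The cost is edits to the shells and a few sentences of SAP text. No new data or change in conduct is needed. The downside is fewer nominal p-values to report.
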